#### **12.4.3. Exploratory Endpoints**

- (1) Determine the association of PD-L1 expression in tumor samples and treatment response
- (2) Perform RNAseq and whole exome sequencing (WES), and determine the association of the molecular profile with treatment response,
- (3) Identify and validate blood and tumor biomarkers that are associated with efficacy-related endpoints or toxicity,
- (4) Develop organoids and PDX models whenever feasible, in order to functionally characterize the tumor of origin and perform drug testing

#### **12.4.4 Analysis Population**

**Efficacy Analysis Set (EAS):** all subjects who are centrally confirmed diagnosis of thymic carcinoma and received at least 1 trial treatment. EAS will be used for efficacy analysis.

**Safety set (SS):** all subjects who receive at least one dose of trial treatment and have at least one valid post-baseline safety assessment. The statement that a patient has no AE (on the Adverse Event eCRF) continues a valid safety assessment.

**Per-protocol set (PPS):** consist of a subset of subjects who are compliant with requirements of the Clinical Trial Protocol (CTP). The PPS will include subjects who have an adequate tumor assessment at baseline, a follow-up tumor assessment >6 weeks after starting treatment, and no major protocol deviations

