## 1. Protocol Summary

Full Title:	Phase II study of KN046 in patients with thymic carcinoma who failed immune checkpoint inhibitors
Short Title:	KN046 in thymic cancer with prior IO
Clinical Phase:	II
Principal Investigator:	[name] PhD
Study Description:	This study will assess the safety and efficacy of KN046 in patients with advanced thymic carcinoma who progressed after prior treatment with immune checkpoint inhibitors
Sample Size:	N= 29
Enrollment:	This study will enroll 29 patients
Study Population:	These are patients with advanced thymic carcinoma who have had progression after treatment with chemotherapy and an immune checkpoint inhibitor. They have no prior or current history of autoimmune disorders.
Enrollment Period:	24 months
Study Design:	Open-label, single arm, single center non-randomized Phase II study to investigate the efficacy and safety of KN046 in patients with advanced thymic carcinoma who have progressed on prior immune checkpoint inhibitor therapy. Subjects will be treated with KN046 5 mg/kg q2wk
Description of Sites/ Facilities Enrolling	
Participants:	Weill Cornell Medicine/New York Presbyterian Hospital
Study Duration:	7/2024
Participant Duration:	24 months
Study Agent/Device Name	KN046
Intervention Description:	KN046 will be given intravenously at 5 mg/kg every 2 weeks. A cycle is defined as 2 treatments (28 days). Treatment will be until progression or excessive toxicity for up to 2 years.
Primary Objective:	To evaluate the anti-tumor activity of KN046 in subjects with thymic carcinoma as measured by overall response rate
Secondary Objectives:	To assess the safety and tolerability of KN046
Exploratory Objectives:	To explore the association of biomarkers (including, but not limited to, PD-L1 expression, tumor immune microenvironment determined by multiplex IHC, tumor mutational burden (TMB), T-cell inflamed gene expression profile (GEP)) and clinical efficacy parameters
	To characterize the safety laboratory results (AChR autoantibody and CPK) and the occurrence of adverse events of interest
Endpoints:	Response rate, progression-free survival, overall survival

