### **10. Measurement of Effect**

#### **10.1 Response Criteria**

RECIST v1.1 will be applied by the site as the primary measure of tumor assessment and response and as the basis for protocol guidelines related to disease status (e.g., discontinuation of study treatment).

Radiological scans of all suspected sites of disease will be performed utilizing the same method and technique throughout the study. Target lesions should demonstrate the patient's baseline tumor burden and will be selected based on size (i.e., lesions with the longest diameter), and suitability for accurate repeat assessment.

The following should be performed:

- PET-CT scans are required for all patients at Screening, at the time of best response, and as clinically indicated
- Chest, abdomen, and pelvis CT (Chest CT and Abdomen/Pelvis MRI acceptable) are required for all patients every 2 cycles for the first year and then every 4 cycles for the second year.

Additional imaging evaluations may be performed at any time if there is symptomatic evidence suggesting the possibility of disease progression based on clinical symptoms or physical examination.

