### **12. Statistical Considerations**

#### **12.1 Study Design/Endpoints**

This is an open-label, single arm, single center non-randomized Phase II study to investigate the efficacy and safety of KN046 in patients with advanced thymic carcinoma who have progressed on prior immune checkpoint inhibitor therapy. Subjects will be treated with KN046 5 mg/kg q2wk.

A Simon's two-stage design will be used. Under the optimum design criterion, a sample size of 29 is required to test a null hypothesis of  $H_0: \pi \leq 0.05$  versus an alternative hypothesis of  $H_1: \pi \geq 0.2$  with a one-sided significance level of 0.047 and 80.11% power, where  $\pi$  is the true proportion of successes. This design results in an expected sample size of 17.624 and a probability of early termination of 0.599. If the number of responses is less than or equal to 0 out of 10 subjects in the first stage then the trial will be stopped. If the trial proceeds to the second stage, 29 subjects in total will be studied. If 3 or less responses are observed, then KN046 is rejected.

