#### **12.2 Sample Size/Accrual Rate**

29 subjects are anticipated to be enrolled in this protocol.

A Simon's two-stage design will be used. Under the optimum design criterion, a sample size of 29 is required to test a null hypothesis of  $H_0: \pi \leq 0.05$  versus an alternative hypothesis of  $H_1: \pi \geq 0.2$  with a one-sided significance level of 0.047 and 80.11% power, where  $\pi$  is the true proportion of successes. This design results in an expected sample size of 17.624 and a probability of early termination of 0.599. If the number of responses is less than or equal to 0 out of 10 subjects in the first stage then the trial will be stopped. If the trial proceeds to the second stage, 29 subjects in total will be studied. If 3 or less responses are observed, then KN046 is rejected. A total sample size of 29 subjects are planned.

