## **12.5 Interim Analysis**

Response will be assessed in the first 10 patients and the study will be continued if responses are seen, or discontinued if no responses are seen.

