### **12.6.2 Evaluation of Response**

All subjects included in the study will be assessed for response to treatment if they have received at least *one* treatment. The response rate will be estimated as a binomial proportion with 95% exact Clopper-Pearson confidence interval using exact binomial calculation

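### Does the undefined term for central confirmation leave the response-rate denominator and the 0/10 and 3/29 rules ambiguous?

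*Combined protocol and SAP*

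**What the plan says.** Section 12.4.4 defines the EAS as "all subjects who are centrally confirmed diagnosis of thymic carcinoma and received at least 1 trial treatment" and states that this set serves for efficacy analysis.

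Section 12.6.2 has two sentences. One says who is assessed: "All subjects included in the study will be assessed for response to treatment if they have received at least" one treatment. The other gives the estimator: "The response rate will be estimated as a binomial proportion with 95% exact Clopper-Pearson confidence interval". Neither mentions central confirmation.

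The decision rules count subjects or patients and name no analysis set. Section 12.5 says "Response will be assessed in the first 10 patients and the study will be continued if responses are seen". Section 12.1 stops the trial for 0 responses in 10 and, at 29 patients, says "If 3 or less responses are observed, then KN046 is rejected".

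Enrolment is put at 29 in both the Protocol Summary ("This study will enroll 29 patients") and section 12.2 ("29 subjects are anticipated to be enrolled in this protocol"). No replacement of unconfirmed patients is mentioned. Under section 10.1, "RECIST v1.1 will be applied by the site as the primary measure of tumor assessment and response".

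**The concern.** Central confirmation appears only in 12.4.4. No section says who confirms the diagnosis, on what material or when. In a trial with one centre the word *central* has no obvious meaning. If it referred to a pathology review after treatment starts, a treated patient could leave the EAS but stay in the group described in 12.6.2.

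The rules turn on single responses. If one treated responder were unconfirmed, 1/10 would continue while 0/9 would stop, and 4/29 would pass while 3/28 would be rejected. Because the trial is open-label and the site reads response, such a removal could happen after the response was known. At stake would be a go/no-go decision that depends on which section is read, and a planned power of 80.11% with almost no margin above 80%.

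**Working it through.** **1. The plan's own figures.** Inputs from section 12.1: null rate 0.05, alternative 0.20, stop at 0 of 10, reject KN046 at 3 or fewer of 29. With X1 ~ Bin(10, p) and X2 ~ Bin(19, p),

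P(pass) = Σ over x = 1, 2, 3 of P(X1 = x) · P(X2 ≥ 4 − x), plus P(X1 ≥ 4).

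- p = 0.05: 0.3151 × 0.0665 + 0.0746 × 0.2453 + 0.0105 × 0.6226 + 0.0010 = 0.0210 + 0.0183 + 0.0065 + 0.0010 = 0.0468 (stated 0.047).
- p = 0.20: 0.2684 × 0.7631 + 0.3020 × 0.9171 + 0.2013 × 0.9856 + 0.1209 = 0.2048 + 0.2770 + 0.1984 + 0.1209 = 0.8011 (stated 80.11%).
- Early termination under the null: 0.95^10 = 0.599. Expected size: 10 + (1 − 0.5987) × 19 = 17.624. Both match.

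The design is correct for 10 and 29 analysed patients.

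**2. Where the documents place confirmation of diagnosis.**

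| Section | What it requires |
|---|---|
| 4.2, criterion 3 | Pathologically confirmed thymic carcinoma, with a tumour sample for that confirmation |
| 4.3, criterion 1 | Thymoma and other named entities excluded |
| 6.1, Schedule of Assessments, note 18 | Biopsy at screening unless archival tissue is available; 10 slides |
| 6.1.1 | Pathology reports reviewed during screening to confirm the diagnosis |
| 3.1 | One centre |

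All of these steps belong to entry. No section describes a later review. If confirmation is the entry check, every treated patient is confirmed, the EAS equals the treated set, and step 1 applies unchanged.

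**3. If a later review did remove patients** (an assumption; cut-offs kept, no replacement). The formula of step 1 with reduced stage sizes gives:

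| Stage 1 / total | Alpha | Power |
|---|---|---|
| 10 / 29 | 0.0468 | 80.1% |
| 10 / 28 (one stage-2 patient unconfirmed) | 0.0426 | 78.6% |
| 9 / 28 (one stage-1 patient unconfirmed) | 0.0407 | 76.7% |

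**4. Range over an assumed unconfirmed rate q.** The documents give no rate. If confirmation is independent of response, a treated patient is a confirmed responder with probability p(1 − q). EAS power is therefore the step 1 formula at 0.20(1 − q), and EAS alpha the same formula at 0.05(1 − q). Because the EAS can never hold more responders than the treated set, the two sets disagree on the final decision with probability 0.8011 minus EAS power. At the stage-1 look they disagree with probability (0.80 + 0.20q)^10 − 0.80^10. These stage-1 disagreements overlap with the final ones and should not be added to them.

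| q | EAS alpha | EAS power | Final decision differs (true rate 20%) | Stage-1 look differs (true rate 20%) |
|---|---|---|---|---|
| 0 | 0.0468 | 80.1% | 0 | 0 |
| 1% | 0.045 | 79.5% | 0.6% | 0.3% |
| 2% | 0.044 | 78.8% | 1.3% | 0.5% |
| 5% | 0.040 | 76.8% | 3.3% | 1.4% |
| 10% | 0.034 | 73.0% | 7.1% | 3.0% |

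**5. Who would have to be removed.** The cut-offs are counts of responders. Dropping a non-responder leaves 0 against 1 or more, and 3 against 4, unchanged. It only moves the estimate slightly: 4/29 = 13.8% (95% CI 3.9 to 31.7) against 4/28 = 14.3% (4.0 to 32.7). Dropping a responder can change a decision, but only against KN046.

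**The case for a change.** The strongest case for a change is that the primary decision should not rest on inference. Central confirmation is undefined, 12.6.2 states the estimator without it, and section 6.1.1 speaks of reviewing reports, not tissue. No sentence says that confirmation on tissue is finished before the first dose. A few words would close the matter before the 10-patient look, and one exclusion is enough to take power below 80%.

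The textual point stands: the term is undefined and the cross-reference is missing. The rest is weaker.

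- Section 12.4.4 does name a set for efficacy, and response rate is the primary efficacy endpoint. Plans seldom repeat the set at every rule.
- The first sentence of 12.6.2 can be read as saying whose response is assessed; the second gives the interval method and no denominator. Assessing everyone treated is compatible with analysing the EAS.
- Removal after a known response cannot favour the drug under count-based cut-offs (step 5).
- One route to a higher false-positive rate exists: replacing unconfirmed patients and then counting everyone treated against the cut-off of 3. With 30 patients alpha is 0.051. The plan provides no replacement and fixes enrolment at 29, so this is not a consequence of the plan.
- Treated patients without a follow-up scan are not named as non-responders. Only the per-protocol set requires such a scan, so they stay in the EAS denominator and contribute no response.

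**Conclusion.** The plan needs no change on this point. Followed as written, with diagnosis confirmed at entry and the EAS used for efficacy, it yields one denominator and a decision with the stated operating characteristics (alpha 0.0468, power 80.1%). This rests on reading confirmation as the entry pathology check, the only one the documents describe.

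If that reading were wrong, the effect would be small at low unconfirmed rates: at 1% to 2%, the final decision differs in 0.6% to 1.3% of trials at a true response rate of 20%. It would grow to 7.1% at an assumed 10%, a rate for which the documents give no support. In each case analysed on the EAS without replacement, the cost is lost power and alpha stays below 0.0468. Analysing all treated patients would be equally defensible, so no analysis choice here is wrong. The gap is one of wording: a term left undefined and sections 12.5 and 12.6.2 not pointing back to 12.4.4.

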## **12.5 Interim Analysis**

Response will be assessed in the first 10 patients and the study will be continued if responses are seen, or discontinued if no responses are seen.

## **12.6 Reporting and Exclusions**

### **12.6.1 Evaluation of Toxicity**

All subjects will be evaluable for toxicity from the time of their first treatment with KN046.

### **12.6.2 Evaluation of Response**

All subjects included in the study will be assessed for response to treatment if they have received at least *one* treatment. The response rate will be estimated as a binomial proportion with 95% exact Clopper-Pearson confidence interval using exact binomial calculation

## **13. Adverse Event Reporting Requirements**

Adverse event (AE) monitoring and reporting is a routine part of every clinical trial. The investigator will be required to provide appropriate information concerning any findings that suggest significant hazards, contraindications, side effects, or precautions pertinent to the safe use of the drug or device under investigation. Safety will be monitored by evaluation of adverse events reported by subjects or observed by investigators or research staff, as well as by other investigations such as clinical laboratory tests, x-rays, electrocardiographs, etc.

### **13.1 Adverse Event Definition**

An adverse event (also referred to as an adverse experience) can be any unfavorable and unintended sign (e.g., an abnormal laboratory finding), symptom, or disease temporally associated with the use of a drug, and does not imply any judgment about causality. An adverse event can arise with any use of the drug (e.g., off-label use, use in combination with another drug) and with any route of administration, formulation, or dose, including an overdose.

#### **13.1.1 Investigational Agent or Device Risks (Expected Adverse Events)**

Expected adverse events to monitor for include infusion-related adverse events, hypersensitivity reactions and immune-related adverse events.

### **13.1.2 Adverse Event Characteristics and Related Attributions**

The descriptions and grading scales found in the revised NCI Common Terminology Criteria for Adverse Events (CTCAE) version 5.0 will be utilized for AE reporting. A copy of the CTCAE version 5.0 can be downloaded from the CTEP web site (<http://ctep.cancer.gov>).

- **Attribution** of the AE:

- Definite – The AE is *clearly related* to the study treatment.
- Probable – The AE is *likely related* to the study treatment.
- Possible – The AE *may be related* to the study treatment.
- Unlikely – The AE is *doubtfully related* to the study treatment.
- Unrelated – The AE is *clearly NOT related* to the study treatment.

### **13.1.3 Recording of Adverse Events**

All adverse events will be recorded on a subject specific AE log. The AE log will be maintained by the research staff and kept in the subject's research chart.

### **13.1.4 Reporting of AE to WCM IRB**

All AEs occurring on this study will be reported to the IRB according to the IRB policy, which can be accessed via the following link:

[http://researchintegrity.weill.cornell.edu/forms\\_and\\_policies/forms/Immediate\\_Reportin\\_Poli\\_cy.pdf](http://researchintegrity.weill.cornell.edu/forms_and_policies/forms/Immediate_Reportin_Poli_cy.pdf).

### **13.1.6 Events of Special Interest**

See section 2.4.1

### **13.1.7 Reporting of Pregnancy**

If, following initiation of the study drug, it is subsequently discovered that a study subject is pregnant or may have been pregnant at the time of study exposure, including during at least 24 weeks after product administration, the investigator must immediately notify the Sponsor Medical Monitor/designee of this event and complete and forward a Pregnancy Reporting Form to sponsor within 24 hours of awareness of the event and in accordance with SAE reporting procedures. In the event of a pregnancy in a subject occurring during the course of the study, the subject must be discontinued from KN046 administration immediately.

Follow-up information regarding the course of the pregnancy, including perinatal and neonatal outcome and, where applicable, offspring information must be reported on the Pregnancy Reporting Form.

Any pregnancy that occurs in a female partner of a male study participant should be reported to Alphamab. Information on this pregnancy will be collected on the Pregnancy Reporting Form.

Any abnormal outcome must be reported in an expedited manner, while normal outcomes must be reported within 45 days from delivery

### **13.2 Definition of SAE**

SAEs include death, life threatening adverse experiences, hospitalization or prolongation of hospitalization, disability or incapacitation, overdose, congenital anomalies and any other serious events that may jeopardize the subject or require medical or surgical intervention to prevent one of the outcomes listed in this definition.

Important medical events that may not result in death, be life-threatening, or require hospitalization may be considered serious when, based upon appropriate medical judgment, they may jeopardize the patient or research subject and may require medical or surgical intervention to prevent one of the outcomes listed as serious

#### **13.2.1 Reporting of SAE to IRB**

All SAEs occurring on this study will be reported to the IRB according to the IRB policy, which can be accessed via the following link:

[http://researchintegrity.weill.cornell.edu/forms\\_and\\_policies/forms/Immediate\\_Reportin\\_Policy.pdf](http://researchintegrity.weill.cornell.edu/forms_and_policies/forms/Immediate_Reportin_Policy.pdf).

#### **13.2.2 Reporting of SAE to FDA**

The Principal Investigator must report any suspected adverse reaction or adverse reaction to study treatment that is both serious and unexpected. Unexpected fatal or life-threatening suspected adverse reactions represent especially important safety information and must be reported to FDA as soon as possible but no later than 7 calendar days following the Principal Investigator's initial receipt of the information.

#### **13.2.3 Reporting of SAE to Jiansu**

Institution will send Jiansu copies of any and all serious adverse event reports filed with the FDA or other applicable regulatory authorities, as well as copies of any correspondence with the FDA or other applicable regulatory authorities, regarding any

and all serious adverse events, irrespective of association with the Study Drug(s) in the course of the Clinical Trial, within 7 business days of such report or correspondence being sent to the FDA or other applicable regulatory authorities.

### **13.3 AE/SAE Follow Up**

All SAEs and AEs reported during this study will be followed until resolution or until the investigator confirms that the AE/SAE has stabilized and no more follow-up is required. This requirement indicates that follow-up may be required for some events after the subject discontinues participation from the study.

### **14. Data and Safety Monitoring Plan (DSMP)**

- The WCM DSMB will monitor all aspects of the safety of this trial.
- All applicable adverse events will be captured and reported to the DSMB. Efficacy data in this trial are the biological and imaging endpoints will be batched and not processed until the end of the trial so they will not be reported in real time to the DSMB.
- The study will be submitted to the DSMB for review every 4 months.

### **15. Stopping Rules**

- If severe autoimmune disorders markedly exceed the expected 15%, the study will be terminated. If in the first 10 patients accrued in the stage I of the study, 4 or more patients develop severe autoimmune disorders, accrual to the study will be stopped and an assessment of safety will be performed with the Sponsor.
- Treatment stopping rules for an individual patient include:
  - Disease progression,
  - Significant study intervention non-compliance
  - Pregnancy
  - Intercurrent illness that prevents further administration of treatment,
  - Unacceptable adverse event(s),
  - Patient decides to withdraw from the study, or
  - General or specific changes in the patient's condition render the patient unacceptable for further treatment in the judgment of the investigator
  - Participant lost to follow-up after several attempts to contact subject to schedule study visit.

**16. Appendix A: Guidelines on the management of immune related adverse events**

Only the general principles of treatment for relatively common immune-related adverse events are listed below. Other immune-related toxicities, including rare but severe immune-related toxicity treatments (such as immune-related ocular toxicity and central nervous system toxicity) can be found in ESMO (31) and NCCN (32). Subjects who have been treated for more than 3 weeks with steroids recommend the use of drugs such as sulfamethoxazole/trimethoprim to prevent opportunistic infections such as pneumocystis.

